3.1 Inclusion criteria

- Pathologically proven (either histologic or cytologic) diagnosis of Stage IIIA or IIIB non-small cell lung cancer; [according to AJCC Staging, 7th edition; see Appendix G] within 6 weeks of registration. The patient should have histologically or cytologically confirmed N2 disease.
- Activating mutation in *EGFR*
- No prior chemotherapy or radiation for lung cancer.
- Patients may be potentially resectable or unresectable.
- Stage III A or B disease, including no distant metastases- based on following diagnostic workup:
 - History/physical examination prior to registration.
 - CT Scan of the chest or PET Scan within 28 days of study entry
 - CT Scan of abdomen or MRI of abdomen or Pet Scan within 28 days of study entry
 - An MRI of the brain or Head CT Scan with contrast within 28 days of study entry
 - PET scan within 28 days of study entry
 - Mediastinoscopies are highly recommended.
- Patients must have measurable or evaluable disease.
- ECOG Performance Status 0-2.
- Age \geq 18.
- CBC/differential obtained within 2 weeks prior to registration on study, with adequate bone marrow function defined as follows:
 - Absolute neutrophil count (ANC) \geq 1,500 cells/ul
 - Platelets \geq 100,000 cells/ul
 - Hemoglobin \geq 9.0 g/dl (Note: The use of transfusion or other intervention to achieve Hgb \geq g/dl is acceptable.)
 - Serum creatinine \leq 1.5 x ULN
 - Total bilirubin $<$ 2.0 times the institutional Upper Limit of Normal (ULN)
 - AST and ALT \leq 2.5 x the ULN
 - Women of childbearing potential must have:

- A negative serum or urine pregnancy test (sensitivity $\leq 25\text{IU HCG/L}$) within 72 hours prior to the start of study drug administration
- Persons of reproductive potential must agree to use and utilize an adequate method of contraception throughout treatment and for at least 4 weeks after study drug is stopped prior to study enrollment, women of childbearing potential must be advised of the importance of avoiding pregnancy during trial participation and the potential risk factors for an unintentional pregnancy.
- Ability to take oral medication
- Patient must sign study specific informed consent prior to study entry.

3.2 Exclusion Criteria

- Pleural or pericardial effusion
 - Pleural effusions allowed if one of the following conditions are met: 1) Negative cytology after adequate sampling by thoracentesis 2) Effusion seen on CT scan but not on chest x-ray and deemed too small to tap under CT or ultrasound guidance
- Severe, active co-morbidity, defined as follows:
 - Cardiac Symptoms; any of the following should be considered for exclusion:
 - Uncontrolled angina, congestive heart failure or MI within (6 months)
 - Diagnosed congenital long QT syndrome
 - Any history of clinically significant ventricular arrhythmias (such as ventricular tachycardia, ventricular fibrillation, or Torsades de pointes)
 - Prolonged QTc interval on pre-entry electrocardiogram (> 450 msec)
 - History of significant bleeding disorder unrelated to cancer, including:
 - Diagnosed congenital bleeding disorders (e.g., von Willebrand's disease)
 - Diagnosed acquired bleeding disorder within one year (e.g., acquired anti-factor VIII antibodies)
 - Ongoing or recent (≤ 3 months) significant gastrointestinal bleeding
- Prisoners or subjects who are compulsorily detained (involuntarily incarcerated) for treatment of either a psychiatric or physical (e.g., infectious) illness
- Men and Women who:
 - are unwilling or unable to use an acceptable method to avoid pregnancy for the entire study period and for at least 4 weeks after cessation of study drug, or Women who:

- have a positive pregnancy test at baseline, or
- are pregnant or breastfeeding

4.0 TREATMENT:

4.1 Neoadjuvant erlotinib

Patients will be evaluated by a thoracic surgeon and medical and/or radiation oncologist and be determined to have either locally unresectable disease or potentially resectable disease.

Patients, who are eligible for the study, will be treated with preoperative/ neoadjuvant erlotinib 150 mg PO daily for two months.

Patients will be evaluated with repeat imaging studies (PET/CT or CT C,A,P) and will be evaluated for surgical resection. Patients who had progressive disease or are NOT a surgical candidate will come off the study and will be treated according to standard therapies. Patients may continue on erlotinib (off the study) if this is felt appropriate by the treating physicians. All patients will be followed up for progression free and overall survival.

4.2 Surgery

Patients who had significant clinical down staging and deemed medically fit to tolerate surgery will have surgical resection within 4-6 weeks after last staging imaging studies. Patients will continue on erlotinib until one day prior to surgical resection.

Patients with non-progressive disease who are not going for surgery should have mediastinal restaging done by either EUS/EBUS or mediastinoscopy.

The patient could receive either adjuvant chemotherapy, radiotherapy or both after surgical resection at the discretion of the treating physician. For the patients with unresectable, non-progressive disease, repeat mediastinal staging is required prior to proceeding with either chemotherapy, radiotherapy or both. Patients are also required to have repeat mediastinal evaluation even if the treating physician decides to continue on erlotinib beyond study duration.

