6.1 Schedule of Evaluations

Parameter	Pre-study	Neoadjuvant Erlotinib Q 2wks*** (D1,15,29,43)	Neoadjuvant Erlotinib (D57)	Surgery (within 4-6 weeks from PET/CT scan)	Post-Surgical Follow up ^b	End of Treatment Visit	FU**
History	X	X	X		X		X
Physical examination	X	X	X		X	X	X
Weight	X	X	X		X	X	X
Vital signs	X	X	X		X	X	X
Performance status (ECOG)	X	X	X		X	X	X
CBC, differential, platelet count	X	X	X		X	X	X
, LFTs, Cal, Mg, ^A	X	X	X		X	X	X
Serum HCG ^A	X						
PFTs ^B	X						
AE Evaluation		X	X		X	X	
CT scan chest or total body PET/CT Scan and CT Scan or MRI of Abdomen or total body PET/CT Scan ^c	X		X				Every six month for first year then yearly till 5 years
PET/CT Scan ^d	X		X				
MRI of Brain or CT of Head with contrast [*]	X		If clinically indicated				If clinically indicated
Mediastinoscopy/ EUS/EBUS ^g	X		If clinically indicated###				
Surgical Evaluation	X		X				
Operative & Surgical pathology report					X		
Perioperative morbidity form					X		
EKG ^f	X						
Pill diary		X	X				

^A -Pre-enrollment laboratory tests should be performed within 14 days of study entry. HCG is required only for patients who are women with childbearing potential and must be done within 72 hours prior to start of study drug administration.

^B - PFTs within 8 weeks of study entry

^C - CT Scan of the chest or Pet Scan within 28 days of study entry and a CT Scan or MRI of abdomen through the Liver within 28 days of study entry

*An MRI of the brain with contrast or Head CT Scan within 28 days of study entry

- ^d-PET/CT scan within 6 weeks of study entry is highly recommended and required for operable patients. If a PET scan is performed then a bone scan is not required.
- ^f- EKG within 6 weeks of study entry.
- ^g- Mediastinoscopies are highly recommended for documentation of N2 disease. EUS or EBUS may substitute mediastinoscopy in appropriate clinical setting.
- h- Subjects who do not receive surgery will have an end of treatment visit 30 days (± 3 days) after Post-Treatment Visit.
- **Follow for survival and recurrence every 3 months for first year, every 6 months afterward and document on follow up form.
- *** specified dates +/- 2 working days
- ## required for patients with non-progressive disease NOT undergoing surgery.

7.0 RESPONSE ASSESSMENT:

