Perform periodic liver testing (transaminases, bilirubin, and alkaline phosphatase) during treatment with TARCEVA. Increased frequency of monitoring of liver function is required for patients with pre-existing hepatic impairment or biliary obstruction. Withhold TARCEVA in patients without pre-existing hepatic impairment for total bilirubin levels greater than 3 times the upper limit of normal or transaminases greater than 5 times the upper limit of normal. Withhold TARCEVA in patients with pre-existing hepatic impairment or biliary obstruction for doubling of bilirubin or tripling of transaminases values over baseline. Discontinue TARCEVA in patients whose abnormal liver tests meeting the above criteria do not improve significantly or resolve within three weeks.

Gastrointestinal Perforation

Gastrointestinal perforation, including fatal cases, can occur with TARCEVA treatment. Patients receiving concomitant anti-angiogenic agents, corticosteroids, NSAIDs, or taxane-based chemotherapy, or who have prior history of peptic ulceration or diverticular disease may be at increased risk of perforation. The pooled incidence of gastrointestinal perforation in the 3 monotherapy lung cancer studies was 0.2% in the TARCEVA arms and 0.1% in the control arms. The incidence of gastrointestinal perforation in the pancreatic cancer study was 0.4% in the TARCEVA plus gemcitabine arm and 0% in the control arm. Permanently discontinue TARCEVA in patients who develop gastrointestinal perforation.

Bullous and Exfoliative Skin Disorders

Bullous, blistering and exfoliative skin conditions, including cases suggestive of Stevens-Johnson syndrome/Toxic epidermal necrolysis, which in some cases were fatal, can occur with TARCEVA treatment. The pooled incidence of bullous and exfoliative skin disorders in the 3 monotherapy lung cancer studies was 1.2% in the TARCEVA arms and 0% in the control arms. The incidence of bullous and exfoliative skin disorders in the pancreatic cancer study was 0.4% in the TARCEVA plus Gemcitabine arm and 0% in the control arm. Discontinue TARCEVA treatment if the patient develops severe bullous, blistering or exfoliating conditions.

Myocardial Infarction/Ischemia

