9. Patient refuses to continue treatment (patient will continue to be followed for disease-free survival and overall survival)
10. Death

In this event notify:

Study PI (contact information on cover page of protocol)

Study Coordinator(contact information on cover page of protocol)

Regulatory Coordinator(contact information on cover page of protocol)

Clinical Trials Office: [contact] AND e-mail:

[contact]

***Document the reason(s) for withdrawal on flow sheets. Follow the patient for survival with follow-up forms as dictated by the protocol**

14.0 FOLLOW-UP:

Subjects who undergo surgery will have a post-surgery follow-up visit 30 days (± 3 days) after surgery. Subjects who do not receive surgery will have an end of treatment visit 30 days (± 3 days) after Post-Treatment Visit.

Any adverse event occurred during the study treatment should be monitored by subsequent follow-up visits until resolves to grade 1 or less, or until a new therapy is started.

Subjects who discontinue treatment for any reason, will be followed for survival. In addition off study evaluations will be done when treatment is discontinued -Section 7.0.

15.0 REGULATORY CONSIDERATIONS:

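### Sections 4.1, 4.2, 4.2.2 and the 6.1 calendar disagree on how long erlotinib runs before surgery; if 4.2 applies, about 32-42% of a surgical patient's dosing days have no scheduled safety check or pill diary

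*Combined protocol and SAP*

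**What the plan says.** **Duration.** Section 4.1 says that eligible patients "will be treated with preoperative/ neoadjuvant erlotinib 150 mg PO daily for two months". Section 4.2 says that patients with significant down-staging who are fit for surgery "will have surgical resection within 4-6 weeks after last staging imaging studies", and adds: "Patients will continue on erlotinib until one day prior to surgical resection". Section 4.2.2 allows thoracotomy four weeks after neoadjuvant therapy and does not say whether drug is taken in those weeks.

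**Calendar (section 6.1).** Visits fall on D1, D15, D29, D43 and D57, with a tolerance of "specified dates +/- 2 working days". Adverse event evaluation, CBC, chemistry and pill diary are marked at these visits, and repeat imaging at D57. The next column, "Surgery (within 4-6 weeks from PET/CT scan", has no mark in any row. Adverse event evaluation and laboratory tests return under post-surgical follow-up. The pill diary has no mark after D57.

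**After surgery.** Section 14.0 states: "Subjects who undergo surgery will have a post-surgery follow-up visit 30 days" after surgery, give or take 3 days. The end-of-treatment visit is defined, there and in the calendar notes, only for patients who do not have surgery.

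**General text.** Section 10.1 instructs: "Perform periodic liver testing (transaminases, bilirubin, and alkaline phosphatase) during treatment with TARCEVA". It asks for periodic renal and electrolyte monitoring too. Neither instruction gives an interval. Section 12.1 has adverse events recorded on the case report form throughout the trial, and section 18.4 evaluates toxicity from the first dose.

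**The concern.** Two problems are joined here. First, a site cannot tell from the protocol whether a surgical patient takes erlotinib for about eight weeks or for about twelve to fourteen. Second, if the longer course is intended, the calendar was built for the shorter one: two-weekly checks stop at D57 while dosing goes on.

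Safety of neoadjuvant erlotinib is a secondary objective (sections 1.2 and 18.1). Drug events in the pre-operative weeks that come to light only at the post-surgical visit would be reported alongside surgical complications, which makes attribution harder. That matters because section 18.4 ties suspension of the trial to an excess of post-operative complications. Section 5.1.1 has withholding criteria that depend on bilirubin and transaminase values, and the calendar schedules no test in this window to produce them. The dose taken in the weeks just before resection, where nodal clearance is read, would have no adherence record.

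**Working it through.** The documents state no figure for total exposure or for the share covered by scheduled checks, so there is none to reproduce. The check is a day count.

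**Inputs**
- Last on-treatment visit and staging imaging: D57 (section 6.1).
- Imaging to surgery: 4-6 weeks, i.e. 28-42 days (sections 4.2 and 6.1).
- Last dose: the day before surgery (section 4.2).
- Next scheduled check after D57: 30 ± 3 days after surgery (section 14.0).

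**Formulas**
- Day of surgery = 57 + 7w, where w is the number of weeks from imaging to surgery.
- Last dosing day = 57 + 7w − 1. Dosing starts on D1, so this is also the number of dosing days.
- Dosing days after the last scheduled check = last dosing day − 57.
- Interval to the next scheduled adverse event or laboratory check = 7w + 30.

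| Weeks to surgery | Last dose | Dosing days after D57 | Share | Days from D57 to next check |
|---|---|---|---|---|
| 4 | D84 | 84 − 57 = 27 | 27/84 = 32.1% | 28 + 30 = 58 |
| 5 | D91 | 91 − 57 = 34 | 34/91 = 37.4% | 35 + 30 = 65 |
| 6 | D98 | 98 − 57 = 41 | 41/98 = 41.8% | 42 + 30 = 72 |

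Up to D57 the interval between checks is 14 days.

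**Sensitivity**
- D57 visit moved by 2 days either way: the share runs from 27/86 = 31.4% to 41/96 = 42.7%.
- Post-surgical visit moved by 3 days either way: the interval runs from 28 + 27 = 55 to 42 + 33 = 75 days.
- The wording of 4.2 can also be taken as an upper limit. Surgery at an assumed 2 or 3 weeks gives 13/70 = 18.6% or 20/77 = 26.0%.
- If dosing stops at D57, as 4.1 and one reading of 4.2.2 allow, the share is zero, and the quoted sentence of 4.2 then conflicts with those sections.

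**Could other text supply the missing check?** Section 12.1 expects adverse events to be found through routine protocol review and clinical assessment, but none is scheduled between D57 and surgery. Section 14.0 follows events at later visits, and the first of these is after surgery. Section 4.2.4 covers perioperative complications, not the outpatient weeks before. The audit in section 12.4 takes place within 8 weeks of registration. None of these sets a date in the window.

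**The case against.** The case against the point is substantial, and several parts of it stand.

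- **A reader might infer that these weeks are unmonitored.** The documents do not support that. Sections 12.1 and 12.2 require adverse event recording throughout, 18.4 evaluates toxicity from the first dose, 5.1.1 applies whenever drug is taken, and 10.1 asks for periodic liver and renal tests. What is missing is a scheduled assessment and an adherence record.
- **A reader might infer that the calendar contradicts the periodic-testing instruction.** That instruction has no interval, and a blank cell does not cancel it. The calendar is silent here. The real disagreement is over treatment duration.
- **A reader might apply the figure to the whole trial.** It holds only for patients who reach surgery. Under 4.1, patients with progression and those who are not surgical candidates come off study after the two-month assessment.
- **A reader might use the 37% rate of dose interruption or reduction in section 10.1 to size the problem.** It comes from a study with median treatment of 9.6 months and does not measure this window. Section 10.1 gives median onsets of 15 days for rash, 32 days for diarrhea and 39 days for interstitial lung disease, all before D57. Later events remain possible: the onset range for interstitial lung disease extends beyond 9 months.
- **The Surgery column may mark timing only.** Even the operative report and perioperative morbidity form sit under post-surgical follow-up, and the table as extracted is partly broken, so cell positions call for some caution. But if the column only marks timing, the window still has no visit.

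What the objection does not supply is any text that schedules an assessment, test or diary entry between D57 and the operation.

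**Conclusion.** The point holds as a scheduling gap that depends on an unresolved conflict over treatment duration. If section 4.2 governs, imaging is on D57 and surgery follows 4-6 weeks later, then 32-42% of a surgical patient's dosing days have no scheduled adverse event evaluation, laboratory test or pill diary. The next scheduled adverse event and laboratory check comes 58-72 days after D57. Earlier surgery makes the share smaller. Late capture of pre-operative events is a risk created by the schedule; the documents do not show that it must happen.

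The sample size and the definition of the primary endpoint are unaffected. The change should be made because safety is a stated objective and the edit is small. This review takes no position on which duration is correct.

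**What to change.** 1. Reconcile sections 4.1, 4.2, 4.2.2 and 6.1 so that they give one account of how long erlotinib is given before surgery and how that relates to the timing of the operation.
2. If the reconciled text has dosing run past D57, mark adverse event evaluation, CBC/chemistry and pill diary in the existing Surgery column, to be recorded before the operation.
3. In that case, also state that on-drug adverse event collection runs through the last dose plus 30 days. This matches the 30-day limit already used in section 12.5.

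**Cost.** A calendar edit, one or two sentences of text, and slightly more case report form data.

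**Limits.** One pre-operative record shortens the gap but does not restore the two-weekly schedule, and events and doses since D57 would still be reported in retrospect. The calendar lists surgical evaluation only at pre-study and D57 and no pre-operative study assessment, so the low cost assumes that the record can be taken when the patient attends for the operation.

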4.2.1 Mediastinoscopy

A mediastinoscopy is highly recommended for all patients prior to neoadjuvant therapy for confirmation of mediastinal disease and also for tissue acquisition for EGFR mutation testing.

4.2.2 Pulmonary resection

Thoracotomy may be performed 4 weeks after neoadjuvant therapy. Surgery is performed if post neoadjuvant induction CT scan shows no significant progression of disease. Patients must be medically fit to tolerate surgery as deemed by the operative surgeon (post operative predicted FEV1 > 40% predicted, no severe active comorbidity-see section 3). Complete surgical resection is the goal. This may entail pneumonectomy, bilobectomy, or lobectomy. Any procedure less than lobectomy is not recommended. Intraoperative frozen sections are performed at the discretion of the surgeon (bronchial resection margin is recommended). Reasons for incomplete resection will be documented. Bronchial stump coverage with local vascularized tissue is recommended.

4.2.3 Handling of mediastinal lymph nodes at thoracotomy

At the time of thoracotomy, mediastinal lymph node dissection is performed at the nodal station biopsied positive on prior mediastinoscopy. Either a full mediastinal lymph node dissection or mediastinal lymph node sampling is performed at all other lymph node stations at the discretion of the surgeon. For right sided lesions, this will include lymph node station 2, 4, 7, 8, 9, 10, and 11. Station 12 and 13 will be submitted along with the lung specimen. For left sided lesions, this will include lymph node station 5, 6, 7, 8, 9, 10, and 11. Station 12 and 13 will be submitted along with the lung specimen. On the left side, dissection or sampling of station 2 and 4 are at the discretion of the surgeon.

Proper documentation of mediastinal lymph node sampling in operative report is mandatory for the study. If the specific stations are not sampled, the reason should be documented in operative report. Failure to document mediastinal node sampling will be considered major protocol violation.

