18.1 Study Design/Analytic Plan

- The primary statistical objectives of this single arm open label phase II study to obtain preliminary estimates of the rate of mediastinal nodal clearance and the rate of complete pathological response in patients with stage III NSCLC with EGFR mutations who received neoadjuvant erlotinib and had surgical resection. Historical data from the neoadjuvant studies with chemotherapy or chemoradiotherapy in resectable NSCLC patients had mediastinal nodal clearance between 15-40%. We hypothesize that patients with stage III EGFR mutated NSCLC treated with neoadjuvant erlotinib therapy must have comparable rates of mediastinal down staging and complete path response for this strategy to evaluate further in this subset of NSCLC patients.
- The mediastinal nodal clearance is defined as pathologically negative N2 disease in the final surgical resection specimen or mediastinoscopy. This can be objectively measured and has been confirmed as the best predictor of long term survival in patients with stage III NSCLC treated with neoadjuvant therapy and had surgical resection.
- Secondary objectives are to estimate objective overall response rate [ORR, i.e., complete response (CR) + partial response (PR)], disease control rate (CR+PR+SD), the surgical resection rate, the progression free (PFS) and overall survival (OS), and the safety of neoadjuvant erlotinib followed by surgical resection in patients with stage III EGFR mutated NSCLC.
- PFS is defined as the time from randomization until documented tumor progression or death from any cause. PFS is censored at the date of the last follow-up visit for patients who are still alive and who have not progressed. OS is defined as the time from the date of randomization to date of death due to any cause.
- Response rates will be summarized by computing proportions and corresponding 95% confidence intervals. Time to event endpoints will be analyzed using standard survival analytic methods, including the Kaplan-Meier approach for estimating the survival distributions. Median time to event and 95% confidence intervals will be estimated from the Kaplan-Meier curves. All primary and secondary analyses will be based on the intent-to-treat principle.

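### A left-sided station 2 or 4 proven positive by EBUS or EUS at baseline need not be re-examined for the patient to meet the clearance definition, so the primary endpoint can be inflated

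*Combined protocol and SAP*

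**What the plan says.** **Endpoint.** Section 18.1: "The mediastinal nodal clearance is defined as pathologically negative N2 disease in the final surgical resection specimen or mediastinoscopy". It sets no condition on which stations were examined and does not say how to score a baseline-positive station with no post-treatment tissue.

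**Baseline proof.** Section 3.1: "The patient should have histologically or cytologically confirmed N2 disease". Section 4.2.1: "A mediastinoscopy is highly recommended for all patients prior to neoadjuvant therapy", so it is advised, not required. Section 6.1, footnote g: "EUS or EBUS may substitute mediastinoscopy in appropriate clinical setting".

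**Surgery.** Section 4.2.3 has four relevant parts:
- At the involved station, "mediastinal lymph node dissection is performed at the nodal station biopsied positive on prior mediastinoscopy".
- At the remaining stations, the surgeon performs either dissection or sampling. The list is 2, 4 and 7 to 11 on the right, and 5 to 11 on the left.
- "On the left side, dissection or sampling of station 2 and 4 are at the discretion of the surgeon".
- "If the specific stations are not sampled, the reason should be documented in operative report". Failure to document nodal sampling is a major protocol violation. Neither rule bears on scoring.

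**Patients not operated on.** Section 4.2 asks for mediastinal restaging by EUS/EBUS or mediastinoscopy if the disease has not progressed. It names no stations.

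**The concern.** The duty to dissect the involved station depends on how that station was proven. If mediastinoscopy proved it, the duty applies. If EBUS or EUS proved it, the station joins the remaining ones, and left stations 2 and 4 are not on the left-sided list.

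Take a left-sided tumour with left station 4 positive on EBUS at entry. At surgery, stations 5 to 11 are taken and are negative, and station 4 is left alone. The plan has been followed and no examined N2 node is positive. Section 18.1 contains nothing that stops this patient being counted as a success, although the one station known to be diseased was not re-examined.

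The possible error runs one way. Disease left in an unexamined station can turn a failure into a success but not the reverse. The same count drives the first-stage decision (go on with more than 3 of 19) and the final one (more than 12 of 55).

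**Working it through.** **1. Which baseline-positive stations are exposed?**

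| Baseline-positive station | Proven by | What 4.2.3 requires at surgery |
|---|---|---|
| Any station except left 2 or 4 | mediastinoscopy | dissection |
| Left 2 or 4 | mediastinoscopy | dissection under one sentence, surgeon's discretion under another: a contradiction |
| Right-sided listed station, or left-sided listed station | EBUS/EUS | dissection or sampling; unexamined only through a documented omission |
| Left 2 or 4 | EBUS/EUS | surgeon's discretion: may go unexamined within the plan |

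Only the last row lets a plan-compliant operation leave the known station unexamined. In every row, 18.1 lacks a scoring rule if the station was in fact not taken.

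**2. Reproduce the design (section 18.2).** Inputs: null rate 15%, alternative 30%, stop at 3 or fewer of 19, negative at 12 or fewer of 55. For an observed success rate q:

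- P(stop at stage 1) = P(Bin(19, q) ≤ 3)
- P(go) = Σ over x = 4 to 19 of P(Bin(19, q) = x) × P(Bin(36, q) > 12 − x)

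| q | P(stop at stage 1) | P(go) | Plan states |
|---|---|---|---|
| 0.15 | 0.684 | 0.0477 | 68.4%; type I error 0.05 |
| 0.30 | 0.133 | 0.8006 | 13.3%; power 80% |

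The plan's figures reproduce.

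**3. Effect of false clearance.** Let f be the share of truly uncleared patients who are scored as cleared. At a true rate of 15%, q = 0.15 + 0.85f, and the expected number of false clearances in a full 55 is 55 × 0.85 × f. The documents give no value for f, so the values below are assumptions.

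| f (assumed) | q | False clearances in 55 | P(stop at stage 1) | P(go) |
|---|---|---|---|---|
| 0 | 0.150 | 0 | 0.684 | 0.048 |
| 1% | 0.1585 | 0.5 | 0.645 | 0.068 |
| 2% | 0.167 | 0.9 | 0.605 | 0.094 |
| 5% | 0.1925 | 2.3 | 0.488 | 0.204 |
| 10% | 0.235 | 4.7 | 0.315 | 0.460 |

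As a guide to what f means: if 10% of uncleared patients have an exposed station and 10% of those are scored as cleared, f = 0.10 × 0.10 = 1%. Shares of 20% and 25% give f = 5%.

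**4. Price of the strict rule.** Suppose a share g of truly cleared patients lack the required specimen and are scored as failures. At a true rate of 30%, q = 0.30 × (1 − g). With g = 5%, q = 0.285 and power falls from 80.1% to 74.0%. With g = 10%, q = 0.27 and power is 66.7%. These g values are also assumptions.

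**The case against.** The strongest reply is that the route is narrow. A patient is miscounted through it only if all of the following hold: the patient is operated on; the tumour is left-sided; station 2 or 4 was involved; EBUS or EUS proved it although mediastinoscopy is recommended; the surgeon left it alone; disease remains there; and every examined N2 station is negative. Patients who progress, or who are not surgical candidates, never come under 4.2.3. This stands. It makes small values of f more plausible than large ones, and the 46.0% figure should not be read as a forecast.

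Three stronger readings are tempting, and the documents do not support them:

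- *Any station proven by EBUS or EUS can be skipped.* The listed stations are still to be dissected or sampled, and the natural reading is that the surgeon chooses between those two. The rule on recording a reason explains an omission; it does not authorise one.
- *A left station 2 or 4 may be omitted whatever the baseline method.* If mediastinoscopy proved it, the first sentence calls for dissection. The two sentences then conflict, which is different from permission to omit.
- *The word joining the two limbs of 18.1 lets a negative post-treatment mediastinoscopy outrank positive nodes at thoracotomy.* The limbs most naturally match operated and non-operated patients, and calling the resection specimen final supports its taking precedence. A clarifying sentence is enough.

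It may also be said that a station with no post-treatment pathology is not pathologically negative. That is a fair reading, but 18.1 does not state it. The opposite reading is also open, and the choice would be made when outcomes are already known.

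**Conclusion.** The concern holds in a limited form. Section 18.1 does not require the baseline-positive station to be re-examined, and the wording of 4.2.3 and 6.1 leaves one plan-compliant case in which it is not: a left station 2 or 4 proven by EBUS or EUS. The direction is certain, since this route can inflate the clearance rate and cannot deflate it. The documents do not fix the size, so it would be wrong to say that the endpoint is inflated by a known amount.

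The design has little room for such errors. About one false clearance in a full 55 (f = 2%) takes the false-go probability from 4.8% to 9.4%, roughly double. That rests on a true rate of 15%, on the two-stage rule being applied as written, and on an assumed f. Because the affected group is plausibly small, this is a correction that should be made, preferably before the first-stage result is read, but it does not invalidate the design.

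**What to change.** - **Section 18.1, scoring.** Count a patient as cleared only if every mediastinal station that was pathologically positive at baseline, by mediastinoscopy, EBUS or EUS, has a negative post-treatment specimen. Score an unexamined baseline-positive station as not cleared in the primary analysis, and add a sensitivity analysis that relaxes this.
- **Section 18.1, precedence.** State that the resection specimen prevails when there is also a post-treatment mediastinoscopy.
- **CRF.** Record baseline-positive stations by number.
- **Sections 4.2.3 and 6.1.** Reconcile the sentence on the station proven at mediastinoscopy with the sentence on left stations 2 and 4, and both with footnote g. Which surgical procedure to use is for the investigators; the scoring rule does not prescribe one.

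The cost is wording and one CRF field. The real downside is that some truly cleared patients without the specimen will count as failures, which loses power as shown in step 4 of the working. The sensitivity analysis would show how much the result depends on them.
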